### Analysis Windows

Participant visits might not occur on protocol-specified days. Therefore, for the purposes of analysis, observations will be assigned to analysis windows. In general, the baseline value will be the last non-missing value on or prior to the first dose date of study drug. HCV RNA and safety laboratory data collected up to the last dose date +  $\leq 3$  days are considered on-treatment data. HCV RNA and safety laboratory data collected after the last dose date +  $> 3$  days are considered post-treatment data.

The following days are based on treatment start date and stop date for the on and post treatment period, respectively.

#### On-treatment

Nominal visit	Standard monitoring arm			Simplified monitoring arm		
	Nominal day	Lower Limit	Upper Limit	Nominal day	Lower Limit	Upper Limit
Baseline	1	NA	1	1	NA	1
Week 4	28	21	42	NA	NA	NA
Week 8	56	43	59	NA	NA	NA

\*The protocol specifies that the visit window for Week 4 and Week 8 is plus or minus 3 days.

#### Post-treatment

Nominal visit	Standard monitoring arm			Simplified monitoring arm		
	Nominal day	Lower Limit	Upper Limit	Nominal day	Lower Limit	Upper Limit
PT week 12	84	70	NA	84	70	NA

\*The protocol specifies that the visit window for Post Treatment Week 12 is plus or minus 14 days. As the post treatment week 12 visit is the final scheduled study visit, the upper limit for the post-treatment week 12 visit will not be specified, and instead will be set at study close.

## **PARTICIPANT DISPOSITION**

### **Recruitment**

The following dates will be presented to define the period of recruitment and follow-up:

- I. first and last participant screened
- II. first and last participant baselined
- III. first and last participant to complete post treatment week 12

### **Participant Enrolment and Disposition**

A summary of participant disposition will be provided overall and by study arm (Table 1). The total number of participants who were screened, enrolled (randomised) and treated will be depicted by a flowchart (Figure 2). Reasons for participant exclusion, including screen failure and loss to follow up, will be summarised (Table 2, Table 3, Table 4).

### **Protocol violations/exemptions**

Number, proportion, type and reason for any protocol violations will be described (Table 5). For this purpose, a protocol violation/exemption will be defined as any person who was enrolled in the study despite failing an inclusion criterion and/or meeting an exclusion criterion.

**Table 1. Recruitment and follow-up**

Participant disposition	Total N (%)	Standard N (%)	Simplified N (%)
Total participants screened, n		NA	NA
Participants screened and excluded, n		NA	NA
Participants allocated to treatment (randomised), N			
Commenced allocated treatment, n/N (%)			
Did not commence allocated treatment, n/N (%)			
Treated Participants			
Completed allocated treatment course, n (%)			
Discontinued treatment, n (%)			
Lost to study follow-up, n (%)			
Study follow up			
Completed study follow up, n (%)			
Did not complete study follow up, n (%)			
Population for analysis			
Intention-to-treat, n			
Modified intention-to-treat, n			
Modified intention-to-treat virological-failure, n			
Per protocol, n			

**Table 2. Reasons for screen failure**

Participant disposition	Total N (%)
Total participants screened, n	
Participants screened and excluded, n	
Screen fail participants who did not meet eligibility criteria	
List reasons (inclusion and exclusion criteria)	
Participants who met eligibility criteria but were not enrolled	
List reasons for not being enrolled	
Lost to follow up	
Withdrew consent	
Other	

**Table 3. Proportion lost to follow-up**

[figure not shown]
Study arm	Number randomised	Proportion lost to follow-up (n/N, %)
Standard Monitoring		
Simplified Monitoring		

**Table 4. Reasons for loss to study follow-up**

Study Number	Arm	Date of treatment commencement	Date last follow-up	Reason lost to follow-up

**Table 5. Protocol violations or deviations**

Protocol violations or deviations	Reason	N (%)
Total number with protocol violations or deviations		
Violation of study inclusion or exclusion criteria		
Enrolment errors		

**Figure 2. Participant disposition**

## **BASELINE DATA**

### **Demographic Data and Baseline Characteristics**

Demographic and baseline measurements will be summarized using standard descriptive methods (Table 6, Table 7).

Baseline data will be summarised for the ITT population and by study arm as: number (n) and proportion for categorical parameters; or n, mean and standard deviation (SD), median, Q1, Q3, minimum and maximum for continuous parameters.

Age will be calculated in years at the date of initial study drug administration (baseline).

*P* values will not be reported for differences between the two groups at baseline, since appropriate randomisation methods will have accounted for this. Any differences identified would be due to chance such that a significant *p* value would in reality be representative of a type 1 error. Large differences at baseline (more than half a SD for continuous variables or 10% for categorical variables) will be investigated in a sensitivity analysis.

Prevalence of baseline polymorphisms in NS3 and NS5A will be summarised (Table 8).

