### **10.3 Efficacy analysis**

The primary analysis will compare the randomised treatment arms on an ITT basis (see section 10.4). The primary efficacy endpoint is the proportion of patients with undetectable HCV RNA at 12 weeks post end of treatment. The treatment arms will be considered non-inferior if the lower limit 95% CI of the difference between the two arms does not exceed -6%. There will be no extrapolation of data for the primary endpoint. Patients with missing data will be analysed as missing equals failure. Secondary analyses will compare randomised treatment groups based on available data (mITT Population).

For all secondary endpoints simple pairwise comparisons of the randomised treatment arms will be undertaken for both the ITT and mITT populations.

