**Figure 1 Study Schema**

**Sample size and power**

The study was designed to enrol a total of 375 participants with genotype 1-6 HCV infection who had not received previous HCV treatment and did not have cirrhosis, randomised 2:1 - 250 participants in the simplified monitoring arm and 125 participants in the standard monitoring arm.

With these participant numbers and under the assumption that the proportion achieving SVR12 would be 96% in both arms, the study would have approximately 80% power to show non-inferiority of the simplified monitoring strategy to the standard monitoring strategy, with a lower confidence bound for SVR12 in the standard monitoring arm greater than 90% or with a lower confidence bound for the difference (simplified arm minus standard arm) in SVR12 greater than -6%. The 90% threshold for non-inferiority of the eight weeks glecaprevir/pibrenatasvir with standard monitoring was based on the clinical trial data available at the time of study design (SVR12 96%), minus a 6% non-inferiority margin. The non-inferiority margin of 6 percentage points was selected in accordance with the principles outlined in guidance on conducting non-inferiority trials; the choice of margin ensured minimal to no loss of efficacy.

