## **GENERAL CONSIDERATIONS FOR DATA ANALYSES**

### **Statistical Methods**

Analysis results will be presented using descriptive statistics. For categorical variables, the number (n) and percentage of participants in each category will be presented. For continuous variables, the number of participants (n), mean and standard deviation (SD), median, interquartile range (IQR, Q1-Q3), range (minimum, maximum) will be reported; for inclusion in the manuscript, an appropriate determination will be made depending on the variable, size and distribution of the population studied. Statistical tests will be 2-sided and performed at the 5% significance level, unless specified. For the analysis of categorical outcomes, Chi-squared tests or exact equivalents (for small numbers) will be used. For comparison of continuous measures, t tests or non-parametric equivalents will be used as appropriate for the observed data distribution.

For the primary analysis of non-inferiority, the percentage of participants achieving SVR12 in each arm and the difference in percentages of participants achieving SVR12 between study arms will be calculated with confidence intervals using the normal approximation to the binomial distribution.

Non-inferiority of the 8-week regimen of glecaprevir/pibrentasvir with a simplified monitoring strategy to the 8-week regimen of glecaprevir/pibrentasvir with a standard monitoring strategy with regard to the proportion achieving SVR12 will be shown if the lower bound of the confidence interval for the differences is above the non-inferiority margin of -6 percentage points.

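### The baseline-imbalance trigger for a sensitivity analysis selects factors by chance and prevalence; one pre-specified analysis using the randomisation strata should replace it

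*SAP*

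**What the plan says.** The SAP (Demographic Data and Baseline Characteristics) reports no baseline p-values, reasoning that "Any differences identified would be due to chance". It then sets a trigger: "Large differences at baseline (more than half a SD for continuous variables or 10% for categorical variables) will be investigated in a sensitivity analysis". It does not say which variables are eligible, whether 10% is absolute or relative, what estimator or model the sensitivity analysis uses, or how its result is to be read.

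Protocol section 5.1 stratifies randomisation by country and by genotype (1 versus non-1). The primary comparison (SAP, Statistical Methods; Protocol 10.5) is an unadjusted difference in proportions with a normal-approximation interval, and non-inferiority requires the lower bound to be "above the non-inferiority margin of -6 percentage points". Neither document specifies an adjusted or stratified comparison of SVR12. SVR12 by genotype and HIV serostatus (SAP, Secondary efficacy endpoints) and the subgroups in SAP Table 12 are estimates within each arm.

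**The concern.** If every baseline difference is chance, a rule driven by its observed size leaves chance to decide whether a sensitivity analysis is run and on which variable. Fixed cut-offs also mean very different things for different variables. Half an SD is far outside what randomisation produces at this sample size, whereas 10 points is not unusual for a factor present in half the participants. The rule takes no account of whether a factor predicts SVR12.

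The plan may therefore yield no sensitivity analysis, or one on a factor of no particular relevance with its method settled after the baseline data have been seen by arm. Meanwhile the two factors thought important enough to stratify on enter no between-arm comparison. What is at stake is the usefulness of a supporting analysis, not the primary conclusion.

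**Working it through.** **Inputs from the documents.** Arm sizes: "250 participants in the simplified monitoring arm and 125 participants in the standard monitoring arm" (SAP, Sample size and power). Response: "the proportion achieving SVR12 would be 96% in both arms" (same section). Margin: 6 points. Confidence level: 95% (Protocol 10.3). Thresholds: 0.5 SD and 10%.

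**Assumptions.** The 10% is in absolute points; randomisation is simple; prevalences range from 5% to 50%. The documents give no prevalences.

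**The plan's own figure.** The SAP says "the study would have approximately 80% power to show non-inferiority of the simplified monitoring strategy to the standard monitoring strategy". The SE of the difference is √[0.96 × 0.04 × (1/125 + 1/250)] = 0.0215. Power = Φ(0.06/0.0215 − 1.96) = 79.8%. The stated figure reproduces. The documents give no figure for the trigger itself.

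**Continuous factor measured in everyone.** The SE of the standardised difference is √(1/125 + 1/250) = 0.1095 SD. The threshold is 0.5/0.1095 = 4.56 SE, so P = 2[1 − Φ(4.56)] ≈ 5 in a million. Across 20 such variables this is about 1 in 10,000. For comparison, 95% of chance imbalances lie within 1.96 × 0.1095 = 0.21 SD.

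**Categorical factor.** SE = √[p(1 − p)(1/125 + 1/250)] and P = 2[1 − Φ(0.10/SE)]. The exact column enumerates the two binomials.

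| Assumed prevalence | SE | 0.10/SE | P, normal | P, exact |
|---|---|---|---|---|
| 50% | 0.0548 | 1.83 | 6.8% | 6.2% |
| 30% | 0.0502 | 1.99 | 4.6% | 4.2% |
| 20% | 0.0438 | 2.28 | 2.2% | 2.0% |
| 10% | 0.0329 | 3.04 | 0.23% | 0.20% |
| 5% | 0.0239 | 4.19 | 0.003% | 0.005% |

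Stratification makes the rate lower than this for genotype 1 versus non-1 and for country.

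**Several factors at once.** For five to eight independent factors with prevalence 30% to 50%, the chance that at least one fires runs from 1 − (1 − 0.046)^5 = 21% to 1 − (1 − 0.068)^8 = 43%.

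**The thresholds on one scale.** Ten points divided by √[p(1 − p)] is 0.20 SD at 50% prevalence, 0.33 SD at 10% and 0.46 SD at 5%, against 0.50 SD for continuous variables.

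**Sensitivity to the reading of 10%.** If it is relative, the threshold is 0.1p. At 50% prevalence, 0.05/0.0548 gives P ≈ 36%; at 5%, 0.005/0.0239 gives P ≈ 83%. The pattern for uncommon factors reverses.

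**Effect on the SVR12 difference.** A 10-point imbalance shifts it by 0.10 times the gap in failure risk. An assumed 2% versus 8% gives 0.6 points; 2% versus 12% gives 1.0 point. The Protocol's background figures of 99.1% (genotype 1) and 93.1% (genotypes 4–6) also give 0.10 × 6.0 = 0.6 points.

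**What adjustment gains.** With a binary covariate, the variance falls from 0.96 × 0.04 to the within-group average. At 50% prevalence and assumed failure risks of 2% and 6%, this is (0.0196 + 0.0564)/2 = 0.0380 against 0.0384, a 1.0% reduction, and power becomes 80.2%. Two other illustrations (30% prevalence, 2% versus 8.7%; 10% prevalence, 3% versus 13%) reduce variance by up to 2.4%, with power up to 80.8%. Expected failures are 0.04 × 125 = 5 and 0.04 × 250 = 10, so 15 in all.

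**The case against.** The rule is confined to large differences, so rarity is what it is meant to deliver, and under valid randomisation any trigger fires only by chance. That stands as far as it goes: no single common factor fires often. It does not rescue a rule whose strictness depends on variable type and prevalence.

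A reader might infer that the SAP contradicts itself. It does not, strictly: one can reject baseline significance tests and still examine a chance difference that is large. The weakness is in what the rule selects.

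A reader might infer that the rule commits the trial to a data-driven adjusted model. The text says only that differences will be investigated; it names no model. The fair criticism is that method and variables are left open until after the data are seen.

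A reader might infer that factors such as genotype, HIV status, fibrosis and HCV RNA go unexamined. They do not. SVR12 by arm is planned in those subgroups whatever the imbalance, although descriptively. Nor is it true that the trigger cannot reach them: a common fibrosis category could fire it. CD4 count, recorded only in participants with HIV, could too. If 5% to 10% of participants have HIV (assumed), the arms hold about 6.25 and 12.5, or 12.5 and 25, and half an SD is 1.02 or 1.44 SE, a chance of about 31% or 15%.

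Finally, the choice of covariates beyond the strata is a preference. The documents give no evidence that baseline HCV RNA predicts SVR12, and missing outcomes count as failures, which virological factors need not predict.

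**Conclusion.** The point holds as a minor improvement. The trigger picks factors by chance and prevalence, and no planned SVR12 comparison uses the stratification factors. The firing rates rest on reading 10% as absolute, on simple randomisation at 125:250 and on assumed prevalences. Under a relative reading the uncommon-factor result reverses, which itself shows that the rule is under-specified.

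A reader might go further and infer that the non-inferiority conclusion or its error rate is at risk. The documents do not support that: the primary test is the unadjusted ITT difference, which this rule cannot alter. Plausible shifts are about 0.6 to 1.0 points against the 6-point margin, and adjustment moves power only from 79.8% to about 80.2–80.8% in the illustrations. The benefit is mainly that the analysis is fixed in advance.

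**What to change.** Before database lock, delete the trigger sentence and keep baseline differences descriptive. In its place pre-specify one sensitivity analysis, run whatever imbalance is observed: the SVR12 risk difference (simplified minus standard) in the ITT population with its 95% CI, stratified or adjusted by genotype (1 versus non-1) and country. A Mantel-Haenszel risk difference would serve. State beforehand how sparse countries are pooled and that the result supports, and does not replace, the primary test. Log10 baseline HCV RNA is an optional addition and would need a model-based estimator.

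The cost is a few lines of SAP text and one analysis. The limitation is that about 15 expected failures allow only two or three factors, which is a reason to name them now.

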**Table 6. Baseline characteristics (ITT population)**

Variable	Total study population (N=XXX)	Standard arm (N=XXX)	Simplified arm (N=XXX)
Age, median (range)			
Gender, n (%)			
Male			
Female			
Transgender			
Ethnicity, n (%)			
White			
Asian			
Black			
Other			
BMI, median (range)			
HCV genotype/subtype, n (%)			
Genotype 1			
1a			
1b			
1, not specified			
Genotype 2			
2a			
2b			
Genotype 3			
3a			
Genotype 4			
Genotype 5			
Genotype 6			
Genotype mixed			
Specify			
Genotype indeterminate			
HCV RNA, IU/mL			
Quantitative, median (range)			
Log 10 , median (range)			
HIV infection, n (%)			
Opioid substitution therapy, n (%)			

**Table 7. Baseline viral characteristics**

Baseline characteristics	Total study population (N=XXX)	Standard arm N=XXX	Simplified arm N=XXX
HCV			
Fibrosis stage determination, n (%) Transient elastography (Fibroscan) APRI			
Median liver stiffness measurement (Fibroscan®), kPa (range)			
Median APRI (range) APRI (by category), n (%) <0.5 (significant fibrosis unlikely) 0.5-1.5 (significant fibrosis likely)			
Fibrosis stage, n (%) No or mild fibrosis (F0/F1; LSM <7.1 kPa or APRI <0.5) Moderate fibrosis (F2; LSM 7.1-9.4 kPa or APRI 0.5 – 1.5) Severe fibrosis (F3; LSM 9.5-12.4 kPa)			
HIV			
HIV infection, n (%) CD4 count (10  /L), median (IQR) HIV VL ≤50 at screening, n (%) On cART, n (%) Specify regimen - list			

Abbreviations: Combination antiretroviral therapy (cART)

**Evaluation of fibrosis stage**

If more than one measure was used, the hierarchy is as follows:

1. Transient elastography (FibroScan) 
2. APRI

**Table 8. Prevalence of polymorphisms in NS3 and NS5A at baseline**

Polymorphism, n (%)	Total study population N=XXX	Standard arm N=XXX	Simplified arm N=XXX
Any NS3	N	N	N
Q80K/R R155T A156G/T/V A166T D/Q168A/K/L/R			
Any NS5A	N	N	N
K/Q/S24R/F M/L/F28A/G/K/T/V Q/R/K/A30D/E/R L/M/V31M P/H58D/T Y/T93H/N			

Baseline polymorphisms detected by Sanger sequencing at the following amino acid positions:

NS3: 36, 56, 155, 156, 166, 168

NS5A: 24, 28, 30, 31, 58, 93

## STUDY ENDPOINTS

**Table 9. Study endpoints and outcomes**

Primary endpoint	Non-inferiority of simplified on-treatment monitoring to standard on-treatment monitoring (ITT population)	Included in primary analysis
Secondary endpoints	Non-inferiority of simplified on-treatment monitoring to standard on-treatment monitoring (mITT population)	Included in primary analysis
	Non-inferiority of simplified on-treatment monitoring to standard on-treatment monitoring (per-protocol population)	Included in primary analysis
	Virologic failure	Included in primary analysis
	On-treatment adherence	Included in primary analysis
	Early treatment discontinuation	Included in primary analysis
	SVR12, by genotype	Included in primary analysis
	SVR12, by HIV serostatus	Included in primary analysis
	Adverse events	Included in primary analysis
	Laboratory abnormalities	Included in primary analysis
	Unscheduled clinic visits	Included in primary analysis
	Change from baseline in patient reported outcome summary measures	Included in primary analysis
	Presence of baseline polymorphisms	Included in primary analysis
	Presence of treatment-emergent substitutions in patients with virologic failure	Included in primary analysis
Additional pre-specified outcomes	Cost-effectiveness	Not included in primary analysis
	Health practitioner acceptability	Included in primary analysis

### Primary efficacy endpoint

The primary efficacy endpoint is sustained virologic response at week 12 post treatment (SVR12), defined as plasma HCV RNA below the lower limit of quantitation (<10 IU/mL; target not detected [TND] or target detected, not quantifiable [TDnq]) at 12 weeks after the last dose of study drug in the ITT population.

The Aptima HCV Quant Dx assay, version 2.15.5 will be used to measure HCV RNA (Hologic, Inc., Marlborough, MA, USA). The LLOQ for this assay is 10 IU/mL.

The primary efficacy endpoint of SVR12 will be assessed within each arm, and the primary comparison of SVR12 will be for non-inferiority of the simplified monitoring arm compared to the standard monitoring arm (simplified arm minus standard arm).

### **Secondary efficacy endpoints**

Secondary efficacy endpoints include:

- Proportion of participants achieving SVR12 in each arm (in the mITT, mITT-VF and per-protocol populations);
- Proportion of participants with virological failure;
- Proportion of participants who are adherent to treatment and study visits (on-treatment adherence and early treatment discontinuation);

For virological endpoints, the point estimates and 95% exact confidence intervals will be reported by study arm, by HCV genotype and by HIV serostatus.

### **Primary safety endpoint**

The primary safety endpoints are:

- Proportion of participants with common adverse events (reported by greater than 5% of the study population);
- Proportion of participants with at least one severe or potentially life threatening (grade 3 or 4) adverse event;
- Proportion of participants with unscheduled clinic visits.

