## **10.0 Statistics**

### **10.1 Sample Size**

The study is designed to enrol a total of 375 patients: 125 in the standard arm and 250 in the simplified arm. The primary efficacy endpoint of SVR12 will be assessed within each arm, and the primary comparison of SVR12 rates will be for non-inferiority of standard to simplified arms. With these patient numbers, the study has approximately 80% power to show non-inferiority to standard treatment monitoring with a lower confidence bound for the difference (standard – simplified) in SVR12 rates greater than –6% (assuming an SVR12 rate of 96% in both arms).

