**Table 11. Treatment outcome, ITT population**

Outcome	Standard monitoring (N=XXX)	Simplified monitoring (N=XXX)	Difference between arms (95% CI)	P
SVR12, n (%)				
Virologic failure, n (%) On-treatment failure (non-response, breakthrough) Post-treatment relapse		NA NA	NA NA	
Failure for other reasons, n (%) Discontinuation Loss to follow up or missing SVR12 data				

\*Analysis tables will also be presented for the mITT, mITT-VF and PP populations

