**Table 15. Safety parameters – adverse events and treatment discontinuation**

Adverse events	Standard monitoring arm (N=XX)	Simplified monitoring arm (N = XX)
Participants reporting any TEAE up to 30 days after last dose, n (%) Grades 1-2, n (%) Grade 3, n (%) Grade 4, n (%)		
Participants reporting treatment-related TEAE up to 30 days after last dose, n (%) Grades 1-2, n (%) Grade 3, n (%) Grade 4, n (%)		
Serious TEAE, n (%)		
Treatment-related serious TEAE, n (%)		
Treatment discontinuation due to adverse event, n (%)		
Death, n (%)		
Adverse events Common (>5% of study population), n (%) Specify (list)		
Unscheduled clinic visits or phone contact, n (%)		

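### The primary safety endpoints are planned as bare per-arm percentages; Table 15 should add the arm difference with a 95% confidence interval, because no named test could support a conclusion of similar safety for uncommon events

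*SAP*

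**What the plan says.** Under Primary safety endpoint, the SAP lists three endpoints: common adverse events (above 5% of the study population), "Proportion of participants with at least one severe or potentially life threatening (grade 3 or 4) adverse event", and unscheduled clinic visits. That section gives no comparison method, effect measure, interval or margin.

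Their results go into Table 15, "Safety parameters – adverse events and treatment discontinuation", which has one n (%) column per arm and nothing else. Table 16 and the section Summaries of Adverse Events and Deaths likewise plan only numbers and percentages.

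The efficacy tables differ. Tables 10 and 11 have a column whose heading begins "Difference between arms (95% CI" and a P column. The exact intervals planned under Secondary efficacy endpoints are for virological endpoints only.

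The general rules are in the SAP section Statistical Methods. It opens with "Analysis results will be presented using descriptive statistics". It then says "Statistical tests will be 2-sided and performed at the 5% significance level, unless specified" and "For the analysis of categorical outcomes, Chi-squared tests or exact equivalents (for small numbers) will be used".

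Protocol section 10.3 promises simple pairwise arm comparisons for all secondary endpoints, without naming a method. SAP Table 9 lists adverse events and unscheduled clinic visits among the secondary endpoints.

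**The concern.** Both arms take the same drug for the same time. What is randomised is the amount of safety and virological monitoring. Someone deciding whether to adopt the simplified schedule will ask how many more severe events or unscheduled visits it might bring. The SAP handles SVR12 in a form that answers such a question, as a difference with an interval. It does not do so for the outcomes it calls its primary safety endpoints.

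Two outcomes are possible under the plan. Either safety is shown as two percentages with no statement of uncertainty, or the default test of equality is applied to them. The second gives a P value, and for uncommon events at this sample size a P value above 0.05 says little. In neither case does the report show how large an excess under simplified monitoring the data leave open.

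**Working it through.** **Inputs.** Arm sizes: "125 in the standard arm and 250 in the simplified arm" (protocol 10.1). Two-sided 5% level and chi-squared or exact test (SAP, Statistical Methods). The documents give no event rate for any safety endpoint, so every rate below is an assumption and a range is shown. The safety population is everyone who took at least one dose, and no dropout allowance is stated, so 125 and 250 are used.

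**1. The plan's own power figure.** Approximately 80% is stated for SVR12, "assuming an SVR12 rate of 96% in both arms" and with a 6-point margin. Standard error = √[0.96 × 0.04 × (1/125 + 1/250)] = 0.02147. Power = Φ(0.06/0.02147 − 1.960) = Φ(0.835) = 79.8%. The figure is reproduced. It concerns SVR12 only; no power is stated for safety.

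**2. Power of the default test for an assumed doubling.** Let p₁ be the standard-arm rate and p₂ the simplified-arm rate.

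- Pooled rate: p̄ = (125p₁ + 250p₂)/375
- s₀ = √[p̄(1 − p̄)(1/125 + 1/250)]
- s₁ = √[p₁(1 − p₁)/125 + p₂(1 − p₂)/250]
- Power ≈ Φ[(p₂ − p₁ − 1.960 s₀)/s₁]

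For 4% v 8%: p̄ = 0.0667, s₀ = 0.02733, s₁ = 0.02453, so power = Φ[(0.04 − 0.05356)/0.02453] = Φ(−0.553) = 29.0%. The table adds results from enumerating all binomial outcomes.

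| Assumed rates, standard v simplified | Normal approximation | Chi-squared, enumerated | Fisher, enumerated |
|---|---|---|---|
| 2% v 4% | 14.6% | 13.9% | 10.9% |
| 3% v 6% | 21.6% | 21.1% | 18.8% |
| 4% v 8% | 29.0% | 29.2% | 26.2% |
| 5% v 10% | 36.6% | 36.8% | 34.3% |
| 10% v 20% | 70.6% | 72.0% | 69.6% |

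The test is weak for rare endpoints and fair for a doubling from 10%. By the usual two-proportion formula, 80% power at 4% v 8% would need 431 + 862 = 1,293 participants, so a larger trial is not a practical answer.

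**3. What an interval would show.** Suppose 5/125 (4%) v 20/250 (8%) is observed.

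- Test: z = 0.04/0.02733 = 1.46, P = 0.14.
- Wilson limits: standard 1.72% to 9.02%, simplified 5.24% to 12.03%.
- Newcombe lower limit: 4.00 − √[(8.00 − 5.24)² + (9.02 − 4.00)²] = −1.7 points.
- Newcombe upper limit: 4.00 + √[(12.03 − 8.00)² + (4.00 − 1.72)²] = +8.6 points.

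The test is non-significant, yet an excess of more than 8 points remains compatible with the data. The Wald interval is similar, −0.8 to +8.8.

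Now suppose 4% is observed in both arms (5/125 and 10/250). The Newcombe interval is −5.3 to +3.9 points and the Wald interval ±4.2. Even with identical observed rates, an excess close to a doubling is barely excluded or just included, depending on the interval.

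**The case against.** The strongest reply is that the plan means to describe safety, not to test it. Table 15 has no P column, Statistical Methods begins with descriptive presentation, the safety sections speak of summarising, and the safety objective is to evaluate. The non-inferiority hypothesis and margin concern SVR12 alone. This stands: the default test could reach the safety proportions, but nothing in the SAP expressly applies it to them.

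Three stronger readings are tempting, and the documents do not support them.

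- A reader might infer that a non-significant test will be taken as proof of equal safety. Neither document says so, and neither states a hypothesis of equal or non-inferior safety.
- A reader might take 29% as a property of the trial or of all three endpoints. It rests on assumed rates of 4% and 8% and suits an uncommon endpoint such as grade 3 or 4 events. A doubling from 10% has about 72% power.
- A reader might infer that protocol 10.3 obliges a safety comparison that the SAP omits. That sentence sits under efficacy and names the ITT and mITT populations. The protocol lists safety endpoints separately in 10.4, and adverse events come under the sentence only through SAP Table 9.

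Two practical replies also have weight. Anyone can compute an interval from the counts in Table 15, so no information is lost. And a data safety and monitoring board reviews safety, with adverse events collected through the same phone contacts in both arms. These limit the consequence. They do not explain why the trial's own report should leave its primary safety endpoints without an interval when SVR12 has one. Finally, intervals for every common adverse event would multiply comparisons, which is a fair reason to keep those optional.

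**Conclusion.** The point holds as a gap in estimation and reporting, and closing it is a cheap improvement. The primary safety endpoints are to be shown as per-arm percentages with no difference and no interval. If a comparison is made, the only named method is a test of equality that, at 125 v 250, has roughly 14% to 37% chi-squared power for doublings from assumed rates of 2% to 5%. For endpoints that rare, a non-significant result could not support a conclusion of similar safety. For commoner events the limitation is much smaller.

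The power figures depend on the assumed rates. The absence of an interval does not, and it matters equally if description is all that is intended. The SVR12 analysis, the data collected and the sample size are unaffected.

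**What to change.** Add one column to Table 15: difference, simplified minus standard, with 95% CI. Fill it for participants with any grade 3 or 4 event, for unscheduled clinic visits and for discontinuation due to adverse events. Table 15 now lists grades 3 and 4 on separate rows, so a combined row is needed to match the endpoint. Use an interval suited to small proportions, such as Newcombe, and name it, since the SAP's normal approximation for differences is specified for SVR12. Intervals for individual common adverse events can be optional and labelled descriptive.

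Add to the SAP that the trial is not powered for safety comparisons and that safety will be interpreted from the estimated differences and their intervals, not from the absence of a significant test.

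The cost is a table column, a combined row and a short SAP statement, with no new data or participants. The drawback is that the intervals will be wide and will show how limited the safety comparison is.
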